6.2.4 Logistics for Correlative studies

6.2.4.1 PK for vorinostat (vorinostat blood sample handling procedures)

Labeling:

1. Preprinted bar-coded PK sample labels with patient's allocation number and prescribed collection time for the collection tubes.
2. Labels should be attached to the red-top Vacutainer tube and NUNC™ tube before the blood is collected.

Procedures:

1. Label red-top Vacutainer tube (no anticoagulant) with preprinted bar-coded PK sample labels.
2. Collect 5.0 mL whole blood in the labeled red-top vacutainer tube. If blood is being collected from a central or PIC line, collect a 10 mL discard sample first before collecting the actual PK samples.
3. Invert the tube several times and allow the blood sample to clot at room temperature for 30 minutes.
4. Centrifuge the clotted sample at 2,000 x g for 15 minutes at 4°C.
5. Transfer the serum to 3.6 mL NUNC internal thread round bottom cryotubes (NUNC 366524) with the bar-coded PK sample **label** attached.
6. Samples will be stored at -70°C until processing

6.2.4.2 Histone Acetylation in peripheral blood mononuclear cells

Exposure to HDAC inhibitors results in inhibition of histone deacetylation. Histone acetylation (mainly histone H3) has been used as a biological marker of HDAC inhibitor activity. H3 acetylation has been measured successfully in PBMCs in clinical trials using vorinostat and other HDAC inhibitors. We will therefore measure H3 and H4 acetylation in peripheral blood mononuclear cells and in tumor samples of patients before and after treatment with vorinostat.

Mononuclear cells will be obtained prior to treatment initiation and repeated on day 10 (+2) and at the end of cycle 3 (day 17-19). Cells will be isolated from patient blood by centrifugation at 400 x g (Sorvall, HS4 rotor) for 30 min using a Ficoll-Paque gradient (Sigma, St. Louis, MO) as described by Sandor et al. Histone acetylation will be quantified by WB analysis of PBMCs using an acid extraction method to collect nuclear histone proteins.

6.2.4.3 Evaluation of vorinostat effects on tumor tissue acetylation and changes in estrogen receptor expression

Post-treatment tumor samples and PBMCs (as well as the vorinostat PK samples) will be obtained on cycle 3 (days 17-19) after the vorinostat morning dose. Fine needle aspirations (FNA) and core biopsies will be obtained either by an interventional radiologist (visceral disease, lymph node) or a cytopathologist (subcutaneous and skin lesions). Diff-Quick air-dry method (FNA) or touch prep analysis (core biopsies) at time of biopsy will be used to confirm the presence of tumor. Tumor samples will be divided and processed for specific techniques as listed below. An attempt for three cores will be made using the appropriate needle. Tissues will be evaluated for the effects of vorinostat on histone acetylation and estrogen expression (by IHC). For IHC, tumors will be fixed in formalin (1 hour/mm thickness), dehydrated, blocked in paraffin. Five-micron sections will be stained with the appropriate antibodies and visualized by light microscopy. Staining will be evaluated using Adobe Photoshop. As the tumor biopsies may contain a mixture of tumor and surrounding cells, cells will be stained (in addition to ER and H3) with specific antibodies used to distinguish tumor versus non-tumor tissues (e.g. cytokeratin (Keratin (5D3)) for breast cancers. PBMCs histone acetylation and ER expression will be quantified by Western blot.

6.2.4.4 Logistics on Immune modulation

For immune assays we will collect 60cc of blood in green top tubes at baseline and day 10-12 in cycle 1 and on day 17-18 in cycle 3, at the time points specified above for tumor biopsies, FFPE for immune cell infiltrate and a frozen section will be obtained for TCR sequencing.

Exploratory Objectives

1. To define the treatment-induced effects on circulating immune cells.
2. To assess the presence of antigen-specific immune responses to a broad panel of candidate tumor antigens.

At the prespecified endpoints: we will obtain

- Immunohistochemistry and gene expression analysis for immune cell subset quantification and localization within tumors
- Flow cytometry to evaluate changes in intra-tumoral and circulating immune cells
- T cell receptor (TCR) deep sequencing of tissue samples from pre-treatment biopsies and post-treatment biopsies, and post-treatment circulating T cells.
- Immune response mRNA expression analysis to derive signatures associated with tumor response
- Identification of genomic mutations and gene copy aberrations associated with response and resistance to therapy
- Antigen array-base detection of circulating antibody responses

These assays will be obtained in conjunction with [name] lab.

6.3 Usage of Concurrent/Concomitant Medications

6.3.2 Acceptable Concomitant Medications

All treatments that the investigator considers necessary for a subject's welfare may be administered at the discretion of the investigator in keeping with the community standards of medical care. All concomitant medication will be recorded on the case report form (CRF) including all prescription, over-the-counter (OTC), herbal supplements, and IV medications and fluids. If changes occur during the trial period, documentation of drug dosage, frequency, route, and date may also be included on the CRF.

All concomitant medications received within 28 days before the first dose of trial treatment and 30 days after the last dose of trial treatment should be recorded. Concomitant medications administered after 30 days after the last dose of trial treatment should be recorded for SAEs and ECIs as defined in Section 7.2.

Anti-diarrheal and anti-emetic treatment may be given as required, either therapeutically or prophylactically, after such events have occurred in conjunction with a prior dose given without anti-diarrheals or anti-emetics. If needed, efforts will be made to standardize such supportive regimens in agreement with participating Investigators.

Other examples of supportive care medications include prophylactic or therapeutic use of erythropoietin for anemia and bisphosphonates (e.g., pamidronate).

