3.3.1 Inclusion Criteria

1. Pre and postmenopausal women or men with stage IV ER+ breast cancer histological or cytological confirmation

ER-positive tumors

- a. Progressed after at least one line of hormonal therapy

- b. Any number of prior chemotherapy in the metastatic setting
- c. Any number of prior hormonal therapies.
- d. HER2 positive or negative

ER-negative tumors

- e. PD-L1 low, high or unknown
 - f. Progression after prior PD-1 or PD-L1 inhibitors allowed
 - g. HER2 positive or negative
2. 18 years or older.
 3. Eastern Cooperative Oncology Group (ECOG) Performance Status of ≤ 2 .
 4. Understand and voluntarily sign an informed consent prior to any study-related assessments or procedures are conducted and are able adhere to the study visit schedule and other protocol requirements.
 5. Consent to paired tumor biopsy, for accessible tumors
 6. Measureable tumor by RECIST criteria v.1.1
 7. Per Good Clinical Practice, any toxicity related to prior therapies that, in the opinion of the investigator, would potentially be worsened with anti-PD1 therapy should be resolved to less than Grade 1
 8. Adequate organ function within 14 days of study start:
 - o Absolute neutrophil count (ANC) $\geq 1.5 \times 10^9/L$
 - o Hemoglobin (Hgb) $\geq 9g/dL$ (may transfuse if clinically indicated)
 - o Platelets (plt) $\geq 100 \times 10^9/L$
 - o Potassium within normal range, or correctable with supplements;
 - o AST and ALT $\leq 2.5 \times$ Upper Limit Normal (ULN) or $\leq 5.0 \times$ ULN if liver tumor is present;
 - o Serum total bilirubin $\leq 1.5 \times$ ULN
 - o Serum creatinine $\leq 1.5 \times$ ULN, or 24-hr clearance $\geq 60ml/min$; and
 9. Females of child-bearing potential (defined as a sexually mature women who):
 - o Has not undergone a hysterectomy (the surgical removal of the uterus) or bilateral oophorectomy (the surgical removal of both ovaries) or,
 - o Has not been naturally postmenopausal for at least 24 consecutive months (i.e., has had menses at any time during the preceding 24 consecutive months).

Must have negative serum pregnancy test within 7 days before starting study treatment in females of childbearing potential (FCBP) and willingness to adhere to acceptable forms or birth control (a physician- approved contraceptive method (oral, injectable, or implantable hormonal contraceptive; tubal ligation; intra-uterine device; barrier contraceptive with spermicide; or vasectomized partner).

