Because vorinostat's dose limiting toxicities are anorexia, dehydration, diarrhea, and fatigue, patients should maintain adequate fluid and food intake. Encourage patients to seek a nutritional consult. Treat diarrhea promptly with appropriate supportive care, including loperamide. Instruct patients to begin taking loperamide at the first signs of: 1) poorly formed or loose stool, 2) occurrence of more bowel movements than usual in one day, or 3) unusually high volume of stool. Loperamide should be taken in the following manner: 4 mg at first onset of diarrhea, then 2 mg after each unformed stool. Daily dose should not exceed 16 mg/day. Loperamide should not be taken prophylactically. Advise patients to drink plenty of clear fluids to help prevent dehydration caused by diarrhea. Avoid loperamide if there is the presence of blood or mucus in the stool or if diarrhea is accompanied by fever. If grade 3 or 4 diarrhea develops, discontinue further treatment with vorinostat. Patients should not have taken valproic acid, another histone deacetylase inhibitor, for at least 2 weeks prior to study enrollment.

How Supplied:

Vorinostat is supplied by Merck & Co., Inc. Vorinostat will be provided in a 100-120 tablet bottle. For the purpose of this study, vorinostat will be given at 400 mg per day (4x 100 mg tablets), 5 of 7 days. Please refer to complete prescribing information in the FDA packet insert for storage and handling.

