5.1.1 Dose Modifications and Dosing Delays

The following dose modification rules will be used with respect to potential toxicity. Toxicity will be assessed continuously according to the NCI Common Terminology Criteria for Adverse Events [Version 4.0 \(CTCAE v4.0\)](#)

The following dose modifications should be made for febrile neutropenia, and blood counts obtained on day one of each cycle. If more than one of these conditions applies, use the most stringent (i.e., the greatest dose reduction). **The AE may be due to pembrolizumab or**

vorinostat alone in which case the respective agent should be reduced. If overlapping toxicity is suspected both drugs may be reduced with the potential to re-escalate the non-offending agent. Given the very different nature of pembrolizumab and vorinostat/tamoxifen toxicities, separate tables are shown for individual agents.

No dose modification will be pursued for tamoxifen.

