5.1.1.1 Dose Modifications and Dosing Delays Tables for Drug Related Adverse Events

Hematologic toxicity

Neutropenia:

Neutropenia	Vorinostat	Tamoxifen
Febrile neutropenia		
ANC \geq 1000	100%	100%
ANC: 500-1000	Hold for until \leq grade 2 #, Restart at 75%: 300 mg qd for all subsequent cycles Second occurrence resume at 200 mg qd for all subsequent cycles Third occurrence: remove from study	100%
ANC: 0-500	Hold for until \leq grade 2 or less# Restart at 75%: 300 mg qd for all subsequent cycles Second occurrence resume at 200 mg qd for all subsequent cycles Third occurrence: remove from study	100%

#Patient with a dose delay for more than 3 weeks in the first 2 cycles will need to be replaced for toxicity and efficacy assessments.

Patients who developed a second episode of **febrile neutropenia** despite a dose modification will be removed from study.

Anemia

Hemoglobin	Vorinostat	Tamoxifen
>8 mg/dl	100 %: 400 mg qd	100%

6.5-8 mg/dl	75 %: 300 mg qd	100%
<6.5 mg/dl	50 %: 200 mg qd	100%

An alternative to dose modification would be the use of PRBC transfusion. This is not allowed in cycle one, but may be used at the discretion of the treating physician for subsequent cycles.

Thrombocytopenia

Platelets	Vorinostat	Tamoxifen
>75'000	100 %: 400 mg qd	100%
≤75'000	100 %: 400 mg qd	100%
≤50'000/mm ³	Hold until ≤grade 2 or less Restart at 75%: 300 mg qd for all subsequent cycles Second occurrence resume at 200 mg qd for all subsequent cycles Third occurrence: remove from study_	100%
≤25'000/mm ³	Hold until ≤grade 2 or less Restart at 75%: 300 mg qd for all subsequent cycles Second occurrence resume at 200 mg qd for all subsequent cycles Third occurrence: remove from study	100%

Non-hematological toxicities

Laboratory abnormalities must be clinically relevant and dose and drug related to prompt dose modifications.

Bilirubin	Vorinostat	Tamoxifen
≤1.5 mg/dl	100 %: 400 mg qd	100%
1.6 – 3.0 mg/dl	75 %: 300 mg qd	100%

>3.0 mg/dl	First occurrence: hold until \leq grade 2, 75 %: 300 mg qd Second occurrence: Hold until grade 2 or less, 50 %: 200 mg qd	100%
AST/ALT	Vorinostat	Tamoxifen
\leq 2.5 x ULN	100 %: 400 mg qd	100%
2.5-5 x ULN	First occurrence: 75 %: 300 mg qd Second occurrence: 50 %: 200 mg qd	100%

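### The vorinostat anemia table gives hemoglobin cut-offs in mg/dl instead of g/dL, so no reduction row can apply as printed; the loperamide wording also needs aligning

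*Combined protocol and SAP*

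**What the plan says.** **Hemoglobin.** The entry criterion in 3.3.1 reads "Hemoglobin (Hgb) $\geq 9g/dL$ (may transfuse if clinically indicated". The anemia table in 5.1.1.1 keeps vorinostat at 400 mg above 8, reduces it to 300 mg between 6.5 and 8, and reduces it to 200 mg below 6.5. All three rows carry the unit mg/dl. A note under the table offers red-cell transfusion as an alternative to dose reduction, but not in cycle 1.

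**Antidiarrheals.** Section 6.3.2 says "Anti-diarrheal and anti-emetic treatment may be given as required, either therapeutically or prophylactically", but only once the event has occurred with an earlier dose that was given without such treatment. Section 4.1.2, under patient care implications for vorinostat, says "Loperamide should not be taken prophylactically", and the gastrointestinal part of 5.1.1.1 repeats that sentence.

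**Neutropenia, for context.** The two lower ANC rows in 5.1.1.1 say "Second occurrence resume at 200 mg qd for all subsequent cycles", with removal at the third occurrence. A sentence below the table says that patients with a second episode of febrile neutropenia "despite a dose modification will be removed from study". Section 5.1.1 introduces the tables with "The following dose modifications should be made for febrile neutropenia, and blood counts obtained on day one of each cycle".

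**The concern.** The anemia table is the only place where the protocol links a hemoglobin value to a vorinostat dose. If its cut-offs cannot be reached, the rule gives no instruction for any patient whose hemoglobin falls on treatment. The gap matters most in cycle 1, when transfusion is not available as the alternative. Section 5.1.1 does tell investigators in general terms to reduce the agent responsible for an adverse event, but it gives no hemoglobin threshold and no dose.

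The antidiarrheal wording raises a smaller question. Loperamide is the only antidiarrheal that the protocol names. A site that reads 6.3.2 alone could give it preventively after a first episode of diarrhea and so depart from 4.1.2 and 5.1.1.1. Diarrhea is listed among vorinostat's dose-limiting toxicities, and it is also a sign to watch for pembrolizumab enterocolitis (5.1.1.2), so the instruction should be the same wherever it appears.

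**Working it through.** **Hemoglobin unit.** The inputs are the cut-offs 8 and 6.5 mg/dl (5.1.1.1, anemia table) and the entry floor of 9 g/dL (3.3.1, item 8). The conversion is 1 g/dL = 1,000 mg/dL.

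- Upper cut-off: 8 / 1,000 = 0.008 g/dL.
- Lower cut-off: 6.5 / 1,000 = 0.0065 g/dL.
- Entry floor: 9 × 1,000 = 9,000 mg/dL.
- Ratio of entry floor to upper cut-off: 9,000 / 8 = 1,125.

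| Row as printed | Vorinostat | Same value in g/dL | Can a patient meet it? |
|---|---|---|---|
| >8 mg/dl | 400 mg | >0.008 | always |
| 6.5-8 mg/dl | 300 mg | 0.0065-0.008 | never |
| <6.5 mg/dl | 200 mg | <0.0065 | never |

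A patient who enters at the floor would need hemoglobin to fall 1,125-fold to reach the first reduction row.

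With the unit changed to g/dL, the rows read >8, 6.5-8 and <6.5 g/dL. They cover the whole range without overlap, and the entry floor of 9 lies inside the full-dose row. No other number in the protocol has to move.

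**Antidiarrheals.** No arithmetic applies; the sections are compared directly.

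| | 6.3.2 | 4.1.2 and 5.1.1.1 |
|---|---|---|
| Drugs covered | antidiarrheals and anti-emetics as classes | loperamide only |
| Force | optional permission | prohibition |
| Condition | event already seen with an earlier, uncovered dose | none stated |

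Prevention before any diarrhea has occurred is not permitted by 6.3.2, so there is no conflict there. Prevention with another antidiarrheal after an episode is permitted by 6.3.2 and not touched by the other two sections. The only case treated differently is loperamide given preventively after an earlier episode: 6.3.2 would allow it, and 4.1.2 and 5.1.1.1 forbid it. Because the permission is optional, withholding loperamide in that case satisfies all three sections.

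**The case against.** **The unit error corrects itself.** Any oncologist will read the table in g/dL, and in that unit the cut-offs fit the entry criterion. This stands as a statement about practice: it is unrealistic to suppose that sites would apply the printed cut-offs. It does not remove the need to correct a dosing table that sites are asked to follow and that audits check against.

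**The antidiarrheal texts can be followed together.** This also stands. What remains is a cross-reference that 6.3.2 lacks.

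**Stronger readings that the documents do not support.**

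- A reader might infer that a second febrile neutropenia is both continued at 200 mg and removed. Section 5.1.1 names febrile neutropenia and day-1 counts as separate triggers, and the sentence below the table deals specifically with a second febrile episode and requires removal. The tie-break in 5.1.1 (apply the most stringent rule) points the same way. It is defined by dose reduction and does not mention removal, so the specific sentence carries more of the weight. The apparent conflict rests on a febrile neutropenia line with empty cells above the ANC rows, and table layout is unreliable in text extracted from PDF.
- A reader might infer that uneven prophylaxis hides diarrhea and distorts the toxicity results. Under 6.3.2 the first episode must occur without prophylaxis, so it is observed. The same section requires concomitant medication to be recorded and provides for standardizing supportive regimens if needed. Section 5.1.1.2 separately requires monitoring for enterocolitis. Section 8 sets no rate threshold for vorinostat toxicity; its six-patient rule concerns grade 3 non-hematologic events clearly related to pembrolizumab.
- A reader might infer a shift in the week-24 response rate because removed patients become failures. One patient in an arm of 29 is 1/29 = 3.4 percentage points, but that is the weight of any single patient. The documents give no frequency for these events. Sections 3.5 and 6.2.2 keep patients who stop for reasons other than progression in disease follow-up, with imaging every 12 weeks, and 8.3.1 analyzes all randomized patients.

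**Conclusion.** The anemia table is wrong as printed. Its hemoglobin cut-offs are 1,000 times too low, and neither reduction row can be met. This rests only on the unit conversion and on the assumption that g/dL was intended, which the fit with the 9 g/dL entry floor makes close to certain. The likely practical effect is small because the slip is easy to recognize, but it lies in an operative safety rule.

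The antidiarrheal point is secondary and narrow: preventive loperamide after an earlier episode is allowed by one section and ruled out by two. It does not make any instruction impossible to follow. The febrile neutropenia text is untidy but not contradictory.

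Nothing here changes alpha, power, sample size or the decision rule in section 8, and no effect on the response rate can be derived from the documents.

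**What to change.** 1. In the anemia table of 5.1.1.1, change mg/dl to g/dL in all three rows.
2. In 6.3.2, add that the permission for preventive antidiarrheals does not extend to loperamide, with a reference to 4.1.2 and 5.1.1.1.
3. Optional: in the neutropenia table, label the repeat-occurrence steps of the ANC rows as non-febrile, so that the removal sentence plainly governs a second febrile episode.

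The cost is a few words in one amendment. No design parameter or analysis needs to be reworked.

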6.3.3 Prohibited Concomitant Medications

Subjects are prohibited from receiving the following therapies during the Screening and Treatment Phase (including retreatment for post-complete response relapse) of this trial:

- Anti-cancer systemic chemotherapy or biological therapy
- Immunotherapy not specified in this protocol
- Chemotherapy not specified in this protocol
- Investigational agents other than Pembrolizumab
- Radiation therapy
 - Note: Radiation therapy to a symptomatic solitary lesion or to the brain may be allowed after consultation with the study PI and Merck.
- Live vaccines within 30 days prior to the first dose of trial treatment and while participating in the trial. Examples of live vaccines include, but are not limited to, the following: measles, mumps, rubella, chicken pox, yellow fever, rabies, BCG, and typhoid (oral) vaccine. Seasonal influenza vaccines for injection are generally killed virus vaccines and are allowed; however intranasal influenza vaccines (e.g. Flu-Mist®) are live attenuated vaccines, and are not allowed.
- Glucocorticoids for any purpose other than to modulate symptoms from an event of clinical interest of suspected immunologic etiology. The use of physiologic doses of corticosteroids may be approved after consultation with the study PI and Merck.

Subjects who, in the assessment by the investigator, require the use of any of the aforementioned treatments for clinical management should be removed from the trial. Subjects may receive other medications that the investigator deems to be medically necessary.

The Exclusion Criteria describes other medications which are prohibited in this trial.

There are no prohibited therapies during the Post-Treatment Follow-up Phase.

6.3.4 Rescue Medications & Supportive Care

Supportive Care Guidelines

Subjects should receive appropriate supportive care measures as deemed necessary by the treating investigator including but not limited to the items outlined below:

- **Diarrhea:** Subjects should be carefully monitored for signs and symptoms of enterocolitis (such as diarrhea, abdominal pain, blood or mucus in stool, with or without fever) and of bowel perforation (such as peritoneal signs and ileus). In symptomatic subjects, infectious etiologies should be ruled out, and if symptoms are persistent and/or severe, endoscopic evaluation should be considered.
 - In subjects with severe enterocolitis (Grade 3), pembrolizumab will be permanently discontinued and treatment with systemic corticosteroids should be initiated at a dose of 1 to 2 mg/kg/day of prednisone or equivalent. When symptoms improve to Grade 1 or less, corticosteroid taper should be started and continued over at least 1 month.
 - In subjects with moderate enterocolitis (Grade 2), pembrolizumab should be withheld and anti-diarrheal treatment should be started. If symptoms are persistent for more than one week, systemic corticosteroids should be initiated (e.g., 0.5 mg/kg/day of prednisone or equivalent). When symptoms improve to Grade 1 or less, corticosteroid taper should be started and continued over at least 1 month. Regarding guidelines for continuing treatment with pembrolizumab, see Section 5.2.
 - All subjects who experience diarrhea should be advised to drink liberal quantities of clear fluids. If sufficient oral fluid intake is not feasible, fluid and electrolytes should be substituted via IV infusion.
- **Nausea/vomiting:** Nausea and vomiting should be treated aggressively, and consideration should be given in subsequent cycles to the administration of prophylactic antiemetic therapy according to standard institutional practice. Subjects should be strongly encouraged to maintain liberal oral fluid intake.
- **Anti-infectives:** Subjects with a documented infectious complication should receive oral or IV antibiotics or other anti-infective agents as considered appropriate by the treating investigator for a given infectious condition, according to standard institutional practice.
- **Immune-related adverse events:** Please see Section 5.6.1.1 below and the separate guidance document in the administrative binder regarding diagnosis and management of adverse experiences of a potential immunologic etiology.

- Management of Infusion Reactions: Acute infusion reactions (which can include cytokine release syndrome, angioedema, or anaphylaxis) are different from allergic/hypersensitive reactions, although some of the manifestations are common to both AEs. Signs and symptoms usually develop during or shortly after drug infusion and generally resolve completely within 24 hours of completion of infusion. Signs/symptoms may include: Allergic reaction/hypersensitivity (including drug fever); Arthralgia (joint pain); Bronchospasm; Cough; Dizziness; Dyspnea (shortness of breath); Fatigue (asthenia, lethargy, malaise); Headache; Hypertension; Hypotension; Myalgia (muscle pain); Nausea; Pruritis/itching; Rash/desquamation; Rigors/chills; Sweating (diaphoresis); Tachycardia; Tumor pain (onset or exacerbation of tumor pain due to treatment); Urticaria (hives, welts, wheals); Vomiting.

Contraception

Pembrolizumab, tamoxifen and vorinostat may have adverse effects on a fetus in utero. Furthermore, it is not known if pembrolizumab has transient adverse effects on the composition of sperm. Non-pregnant, non-breast-feeding women may be enrolled if they are willing to use 2 methods of birth control or are considered highly unlikely to conceive. Highly unlikely to conceive is defined as 1) surgically sterilized, or 2) postmenopausal (a woman who is ≥ 45 years of age and has not had menses for greater than 1 year will be considered postmenopausal), or 3) not heterosexually active for the duration of the study. The two birth control methods can be either two barrier methods or a barrier method plus a hormonal method to prevent pregnancy. Subjects should start using birth control from study Visit 1 throughout the study period up to 120 days after the last dose of study therapy.

The following are considered adequate barrier methods of contraception: diaphragm, condom (by the partner), intrauterine device, sponge, or spermicide. Appropriate hormonal contraceptives will include any registered and marketed contraceptive agent that contains an estrogen and/or a progestational agent (including oral, subcutaneous, intrauterine, or intramuscular agents).

Subjects should be informed that taking the study medication may involve unknown risks to the fetus (unborn baby) if pregnancy were to occur during the study. In order to participate in the study they must adhere to the contraception requirement (described above) for the duration of the study and during the follow-up period defined in section 7.2.2-Reporting of Pregnancy and Lactation to the regulatory agencies and to Merck. If there is any question that a subject will not reliably comply with the requirements for contraception, that subject should not be entered into the study.

7 Reporting and Documentation of Results

